### **9.2.3 Secondary endpoint(s)**

#### **9.2.3.1 Key secondary efficacy endpoint**

##### **IDFS**

IDFS (STEEP criteria) is defined as in the primary endpoint but including second non-breast primary invasive cancer.

A summary of the primary estimated associated with the key secondary endpoint is provided in [Table 9](#).

**Table 9 - Summary of primary estimand of the key secondary endpoint**

Endpoint Category (estimand)	Estimands			
	Endpoint	Population	Intercurrent event(s) handling strategy	Population-level summary (Analysis and missing data handling)
Key secondary objective: to determine whether amcnestrant once a day (QD) improves the invasive disease-free survival (IDFS) when compared to tamoxifen QD in patients with early breast cancer as adjuvant treatment				
Key secondary endpoint (Estimand 2)	IDFS	ITT	
Interruption/discontinuation of study intervention: IDFS will be analyzed based on disease assessments irrespective of study intervention interruption/discontinuation (treatment policy strategy).
 
Start of new therapy prior to IDFS event: IDFS will be analyzed based on disease assessments regardless of whether new therapy is initiated prior to event of interest (treatment policy strategy).
 
IDFS event documented more than 12m+90days after previous disease assessment: IDFS will be censored at the last disease assessment prior to the event (hypothetical strategy).
	
One-sided log-rank test stratified by randomization stratification factors (except geographical regions), as entered in the IRT system.
 
Hazard ratio (HR) and corresponding 95% CI estimated using stratified Cox proportional hazard model
 
The Kaplan Meier estimate of event free probabilities at specified time points, quartiles and corresponding 95% CI from Kaplan Meier method

Analysis of the key secondary endpoint analysis will consist of IDFS comparison between the amcnestrant arm and the tamoxifen arm through a logrank test procedure stratified by the stratification factors (except geographic region to minimize the risk of power loss due to large number of strata and potentially low number of events in some strata) as entered in the IRT.

In order to ensure a strong control of the overall Type I error rate at a one-sided 2.5%, a hierarchical testing strategy will be used. In other words, comparison between arms on the IDFS will be performed only if the primary analysis of the IBCFS is statistically significant. Therefore, a maximum of one formal statistical comparison is planned for IDFS. Otherwise, IDFS will be analyzed descriptively as for other secondary efficacy endpoints.

Same statistical methods and censoring rules as defined for the IBCFS will be used. Sensitivity, supportive and subgroup analyses will be performed as specified in the SAP.

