Section 8.6.2	The total number of blood s-monovette edta 1,2 mL tubes for plasma collected C2 and C7 will be 300.	Increase the number of plasma samples in order to have 100 samples from Chinese patients and 200 from other countries
Section 8.9 and Section 10.5 Appendix 5	Biological samples will be stored for 15 years. Data related to future research will be stored for 25 years.	Clarifications
Section 9.2.1	In Table 7 Timing of analyses, the word "approximately" has been added in the column "Number of events required"	Clarification if the number of events required is not reached in a reasonable timeframe
Section 9.2.2	In the Table 8 and in the text, the level of confidence "95%"/"95 two-sided" for the confidence interval of the hazard ratio removed, respectively.	Clarification considering that the level of confidence will be adjusted for the Type 1 error spent at interim analysis and final analysis
Section 9.3	Cumulative probability to stop for futility under IBCFS HR = 0.76 (false negative rate) added in Table 11 - Summary of IBCFS summary	Request from French competent authorities
Section 10.2 Appendix 2	Other blood tests will include FSH, estradiol, PT/INR and bone turnover markers. If local lab cannot measure bone tumor markers, samples will be shipped to a central lab	Clarifications
Section 10.4 Appendix 4	This appendix includes information on contraception for pre/perimenopausal participants. Both male and female participants must agree to be on GnRH. Female patients must agree to use highly effective methods of contraception during the treatment period until the end of relevant systemic exposure (ie, 5 times of the longest IMP half-life (tamoxifen) plus 6 months period, which corresponds to ~9 months for tamoxifen as per CMDh guidance. Male participants without prior orchiectomy must keep contraceptive measures until 160 days after last IMP dose. Collection of pregnancy information over a period of 6 to 8 weeks however it may be longer if required by local regulations.	Update for female contraception period requested by French ethics committee. Update for male contraception period requested by Belgium and United Kingdom competent authorities.
Section 10.8 Appendix 8	For CHINA: a total of 100 plasma samples was added for PK analysis. Genetic analyses and biomarker research for FFPE at screening is not applicable.	Clarifications

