## **Analysis of main secondary endpoints:**

### Key secondary endpoint (IDFS)

Same statistical methods as defined for the IBCFS will be used. To ensure a strong control of the overall Type I error rate at a one-sided 2.5%, a hierarchical testing strategy will be used. In other words, comparison between arms on the IDFS will be performed only if the primary analysis of the IBCFS is statistically significant.

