**Table 8 - Summary of primary estimand of the primary endpoint**

Endpoint Category (estimand)	Estimands			
	Endpoint	Population	Intercurrent event(s) handling strategy	Population-level summary (Analysis and missing data handling)
Primary objective: to determine whether amcnestrant once a day (QD) improves the IDFS excluding second primary invasive cancers of non-breast origin (IBCFS) when compared to tamoxifen QD in patients with early breast cancer as adjuvant treatment				
Primary endpoint (Estimand 1)	IBCFS	ITT	
Interruption/discontinuation of study intervention: IBCFS will be analyzed based on disease assessments irrespective of study intervention interruption/discontinuation (treatment policy strategy).
 
Start of new therapy prior to IBCFS event: IBCFS will be analyzed based on disease assessments regardless of whether new therapy is initiated prior to event of interest (treatment policy strategy).
 
IBCFS event documented more than 12m+90days after previous disease assessment: IBCFS will be censored at the last disease assessment prior to the event (hypothetical strategy).
	
One-sided log-rank test stratified by randomization stratification factors (except geographical regions), as entered in the IRT system.
 
Hazard ratio (HR) and corresponding CI estimated using stratified Cox proportional hazard model
 
The Kaplan Meier estimate of event free probabilities at specified time points, quartiles and corresponding 95% CI from Kaplan Meier method

Primary efficacy analysis will consist of IBCFS comparison between the amcnestrant arm and the tamoxifen arm through a logrank test procedure stratified by the stratification factors (except geographic region to minimize the risk of power loss due to large number of strata and potentially low number of events in some strata) as entered in the IRT. A one-sided Type I error rate of 2.5% will be used for statistical testing.

The primary analysis of IBCFS will be based on the following censoring rules:

- If none of the IBCFS event is observed before the IBCFS analysis COD, participants will be censored at the date of the last disease assessment documenting no IBCFS event before the COD.
- A participant without an IBCFS event and without any valid postbaseline disease assessments will be censored at the day of randomization (Day 1).

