#### 9.4 SAMPLE SIZE DETERMINATION

For IBCFS, a total of 568 IBCFS events will be needed to reject the null hypothesis using a log-rank test at the one-sided level of 2.5% and 90% power under the assumption of an HR of 0.76. Assuming proportional hazards under an exponential model and based on an anticipated 4-year IBCFS rate of 82% in the tamoxifen arm, this is expected to correspond to a 4-year IBCFS rate of 86% in the amcenestrant arm.

Based on a piecewise enrollment assumption over 24 months as described in [Table 12](#), an IBCFS cut-off date (COD) 60 months after the first participant randomized and an annual dropout rate of 1%, a total of 3738 participants are expected to be randomized in a 1:1 ratio into the amcenestrant and tamoxifen arms.

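### Table 9 fixes the IDFS hazard ratio interval at 95% while the IDFS test level is unstated; either the interval does not match the test or the claimed 2.5% control does not hold

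*Combined protocol and SAP*

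**What the plan says.** In Section 9.2.2, Table 8 describes the IBCFS estimate as "Hazard ratio (HR) and corresponding CI estimated using stratified Cox proportional hazard model", with no level. The summary of changes explains why 95% was taken out there and in the synopsis: "Clarification considering that the level of confidence will be adjusted for the Type 1 error spent at interim analysis and final analysis". In Section 9.2.3.1, Table 9 describes the IDFS estimate as "Hazard ratio (HR) and corresponding 95% CI estimated using stratified Cox proportional hazard model".

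The synopsis says of IDFS: "Same statistical methods as defined for the IBCFS will be used", and the text under Table 9 repeats this. That text also claims strong control of the overall one-sided error at 2.5% through a hierarchy. IDFS is tested only after a significant IBCFS result, and at most once. Section 9.4 places that test at the second interim or the final analysis.

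Section 9.3 and Table 11 give an O'Brien-Fleming-type spending function and one-sided levels of 0.0096 (second interim) and 0.0221 (final), for IBCFS only. No section gives the nominal IDFS level at either analysis.

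**The concern.** An interval reported beside a confirmatory test should have the confidence level implied by that test. The sponsor applied this to IBCFS. The reason given applies equally to IDFS, which can be tested at the same two analyses, but Table 9 kept its 95%.

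If IDFS has to meet a level well below 0.025 at the second interim, the report can show an IDFS test that fails next to a hazard ratio interval that excludes 1. Readers would tend to take that as a positive key secondary result. The two confirmatory endpoints would also carry intervals built on different bases.

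**Working it through.** **Inputs from the protocol.** For IBCFS, "A one-sided Type I error rate of 2.5% will be used for statistical testing" (Section 9.2.2); "90% power under the assumption of an HR of 0.76" and 568 events (Section 9.4); 426 events at the second interim, which is 3/4 of 568; O'Brien-Fleming-type spending (Section 9.3).

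**Assumptions, not in the protocol.** The number of second non-breast primaries, the treatment effect on them, and the correlation between the IBCFS and IDFS statistics.

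**1. Reproduce Table 11.** Spending: α(t) = 2[1 − Φ(z₀.₉₈₇₅/√t)]. At t = 0.75 this is 0.00965, so z = 2.340. Boundary HR = exp(−2 × 2.340/√426) = 0.7971. Solving the bivariate normal with correlation √0.75 gives a final z of 2.0118 (one-sided 0.0221) and HR = exp(−2 × 2.0118/√568) = 0.8447. Power under HR 0.76 is 68.9% at the second interim and 90.0% overall, and 567.5 events are needed for 90%. All agree with Table 11.

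**2. Reading A: IDFS tested once at 0.025 when IBCFS first succeeds.** The matching interval is 1 − 2 × 0.025 = 95%, so Table 9 is consistent with the test. The error rate is not. Having only one IDFS test does not protect it, because IBCFS, which is correlated with IDFS, decides at which analysis the test occurs. Simulating with no IDFS effect and taking the worst case over the IBCFS effect:

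| Assumed correlation | Worst-case one-sided IDFS error |
|---|---|
| 0.80 | 2.8% |
| 0.90 | 2.9% |
| 0.95 | 3.1% |
| 1.00 | 3.6% |

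Every IBCFS event is also an IDFS event, so high correlation is realistic. If IDFS has k times the IBCFS events, the correlation is about √(1/k): 0.98 at k = 1.05 and 0.88 at k = 1.30.

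**3. Reading B: IDFS held to a level that keeps 2.5%, for example the Table 11 levels.** The matching intervals are 1 − 2 × 0.00965 = 98.07% at the second interim and 1 − 2 × 0.0221 = 95.6% at the final. On the log scale the 95% interval has 1.96/2.340 = 0.84 of the required width.

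With D IDFS events, the 95% interval excludes 1 when HR < exp(−2 × 1.96/√D), and the test succeeds when HR ≤ exp(−2 × 2.340/√D). Test and interval disagree between these limits:

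| Second interim, IDFS events | HR range with disagreement |
|---|---|
| 426 | 0.797 to 0.827 |
| 475 | 0.807 to 0.835 |
| 530 | 0.816 to 0.843 |

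Example with 426 events and HR 0.81: SE = 2/√426 = 0.0969 and one-sided p = 0.0148, which fails 0.0096. The 95% interval is 0.670-0.979; the 98.07% interval is 0.646-1.016. At the final analysis with 568 events the range shrinks to 0.8447-0.8483.

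**4. How often, under Reading B.** The IBCFS Z at 426 events has mean −ln(0.76) × √426/2 = 2.83. The IDFS Z is √(1/k) × Z(IBCFS) + √(1 − 1/k) × Z(second primaries). With second primaries unaffected by treatment, k = 1.05-1.30 gives an IDFS HR of about 0.77-0.81. The last column multiplies by 0.689, the chance of IBCFS success at the second interim.

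| Extra events | Disagreement, given IBCFS success at second interim | Of all trials |
|---|---|---|
| 5% | 6.2% | 4.3% |
| 10% | 8.8% | 6.1% |
| 15% | 10.5% | 7.2% |
| 20% | 11.8% | 8.1% |
| 30% | 13.7% | 9.4% |

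With 10% extra events, IDFS fails in 10.5% of these IBCFS successes, and 8.8/10.5 = 84% of the failures would show a 95% interval excluding 1.

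**5. Sensitivity.** Sections 2.2.7 and 2.3.1 link tamoxifen to endometrial and uterine cancers, so second primaries may favour amcenestrant. With an assumed second-primary HR of 0.9, the conditional figure is 4.7-8.4% (3.2-5.8% of all trials). With 0.76 it is 2.3-3.0% (1.6-2.1% of all trials).

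**The case against.** The strongest objection is that the IDFS test level is unknown. Table 11 and the spending function are for IBCFS, and a single IDFS comparison under an overall 2.5% can be read as a test at 0.025, which the 95% interval fits. This stands to the extent that the contradiction cannot be asserted as a fact of the plan. A reader might infer that the protocol already holds IDFS to 0.0096 at the second interim and so will produce conflicting results; the documents do not say that. But the 0.025 reading only moves the problem, since it does not deliver the strong control claimed under Table 9.

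It can also be said that the 95% is simply left over from an amendment that edited only the IBCFS text, that the statement on common methods overrides it, and that the SAP, still to be finalised under Section 9.2, can settle the matter. That is plausible. It is a reason why the change is easy, but as written the table and the text disagree.

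Finally, tests decide significance. Table 11 says so for IBCFS, and nothing makes the IDFS interval a decision rule. That is right, so it would go too far to say that the 95% interval undoes the hierarchy's error control. The risk is one of interpretation.

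**Conclusion.** The point holds in conditional form. Table 9 fixes a level that Table 8 deliberately leaves open, although both endpoints are to be analysed by the same methods, and the protocol gives no IDFS test level against which to judge it. With IDFS at 0.025, interval and test agree but IDFS error can reach about 2.8-3.6% (assumed correlations 0.8-1.0). With IDFS at a level that keeps 2.5%, the 95% interval is too narrow for the test at the second interim.

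On the Table 11 levels, disagreement would occur in about 6-14% of trials that succeed on IBCFS at the second interim, or about 4-9% of all trials. This assumes an IBCFS HR of 0.76 and treatment-neutral second primaries adding 5-30% more events; it is less frequent if second primaries favour amcenestrant. At the final analysis the mismatch is minor (95.6% against 95%).

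Only the error control, reporting and interpretation of IDFS are affected. A reader might infer a flaw in the primary analysis, but the IBCFS error rate, power and sample size reproduce and are unchanged.

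**What to change.** 1. In Section 9.2.3.1 and the SAP, state the one-sided IDFS test level at the second interim and at the final analysis, taken from a spending function that keeps strong control. The same O'Brien-Fleming type as for IBCFS would do: its two boundaries together spend 2.5%, and requiring IBCFS success first can only lower that.
2. In Table 9, replace the 95% for the IDFS hazard ratio with a two-sided interval at 1 − 2 × that level. This is 98.07% at the second interim and 95.6% at the final if the Table 11 levels are adopted.
3. Label any 95% IDFS interval as descriptive, including when IDFS is not formally tested.

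The cost is a few lines of text. If the trial succeeds at the second interim, the reported IDFS interval is about one fifth wider on the log scale (2.340/1.96 = 1.19). If the sponsor had intended to test at 0.025, the lower level also gives up the IDFS claim in the 6-14% of second-interim successes described above, on the same assumptions.

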### 9.2.3.2 Other secondary efficacy endpoints

For all time to event secondary endpoints (DRFS, LRRFS, OS), the HR estimates and corresponding 95% two-sided CIs will be provided using the Cox proportional hazard model stratified by the stratification factors (except geographic region) as entered in the IRT. The time-to-event and quantiles and probabilities of being event-free at different time points (calculated using the Kaplan-Meier methods) as well as corresponding 95% CIs will be presented by treatment arm. The Kaplan-Meier curves will also be provided.

For the endpoint BCSS, the HR estimate and corresponding 95% two-sided CIs will be provided by using Fine and Gray model accounting for competing risks and stratified by the stratification factors (except geographic region) as entered in the IRT. The cumulative incidence of breast cancer-related deaths at different timepoints (calculated using the cumulative incidence function method) as well as 95% CIs will be presented by treatment arm. The corresponding BCSS rates and 95% CIs will be computed as “1 minus cumulative incidence function”. The cumulative incidence curves will also be provided.

Sensitivity, supportive and subgroup analyses will be performed as specified in the SAP.

## **DRFS**

DRFS is defined as the time from date of randomization to the date of the first occurrence of one of the following events:

- Distant recurrence: Metastatic disease-breast cancer that has either been biopsy confirmed or clinically diagnosed as recurrent invasive breast cancer.
- Death attributable to any cause, including breast cancer, nonbreast cancer, or unknown cause.

Same censoring rules as defined for the IBCFS will be used.

## **LRRFS**

LRRFS is defined as the time from date of randomization to the date of the first occurrence of one of the following events:

- Ipsilateral invasive breast tumor recurrence (IIBTR): invasive breast cancer involving the same breast parenchyma as the original primary.
- Loco-regional invasive breast cancer recurrence: Invasive breast cancer in the axilla, regional lymph nodes, chest wall, and skin of the ipsilateral breast.
- Death attributable to any cause, including breast cancer, nonbreast cancer, or unknown cause.
- Invasive contralateral breast cancer.

Same censoring rules as defined for the IBCFS will be used.

## **Overall Survival**

Overall survival is defined as the time from date of randomization to the date of death due to any cause. In the absence of observation of death, survival time will be censored at the last date the participant is known to be alive or at the analysis cut-off date, whichever occurs first.

A summary of the efficacy endpoints analyses is provided in [Table 10](#).

## Breast Cancer-Specific Survival

Breast Cancer-Specific survival is defined as the time from randomization to the date of death attributable to breast cancer cause. Deaths attributable to nonbreast cancer cause or to unknown cause are considered competing risks at the date of death. In the absence of observation of death, survival time will be censored at the last date the participant is known to be alive or at the analysis cut-off date, whichever occurs first.

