### **8.1.3 Overall survival follow-up**

After discontinuation of study treatment, follow-up visits will be performed every 12 months (±45 days) from the last dose of study treatment for survival status and collection of data on post-study anticancer therapies, and disease recurrence for patients who complete or prematurely discontinue study treatment without disease recurrence.

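### BCSS counts unknown-cause deaths as competing even after documented distant recurrence, which understates breast cancer mortality to the extent that such deaths are from breast cancer

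*Combined protocol and SAP*

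**What the plan says.** Section 9.2.3.2 defines the endpoint: "Breast Cancer-Specific survival is defined as the time from randomization to the date of death attributable to breast cancer cause". It then sets the competing events: "Deaths attributable to nonbreast cancer cause or to unknown cause are considered competing risks at the date of death". Nothing in the definition depends on whether the participant had a recurrence.

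The same section says that the hazard ratio "will be provided by using Fine and Gray model accounting for competing risks". It also has "The cumulative incidence of breast cancer-related deaths at different timepoints" reported by arm, with the BCSS rate taken as the complement of that incidence. Table 10 repeats this.

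On status, BCSS is an other secondary endpoint. The hierarchy in section 9.2.3.1 contains only IBCFS and then IDFS, and if IBCFS is not significant: "Otherwise, IDFS will be analyzed descriptively as for other secondary efficacy endpoints". For the other secondary endpoints, section 9.2.3.2 adds: "Sensitivity, supportive and subgroup analyses will be performed as specified in the SAP".

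On data collection, section 8.1.3 describes yearly visits after the end of treatment "for survival status and collection of data on post-study anticancer therapies, and disease recurrence". No section says how cause of death is attributed or adjudicated.

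**The concern.** The rule ignores what the trial knows about the participant. Date and occurrence of distant recurrence are collected because DRFS needs them. A death of unrecorded cause in someone with documented metastatic breast cancer is more plausibly from that disease than not, yet it is classed with non-breast-cancer deaths.

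Some deaths of unknown cause are to be expected:

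- The protocol names the category in the definitions of IBCFS, IDFS, DRFS and LRRFS. Those endpoints count every death, so only BCSS depends on the cause.
- Recurrence ends study treatment (section 7.1.1), so deaths after distant relapse fall mostly in follow-up, where contact is yearly.
- The notes to the schedule of activities (section 1.3) specify on-site visits for participants without recurrence.
- Safety reporting is a weak backup. From 30 days after the last dose it is limited to ongoing related events, ongoing serious events and new related events (section 8.3.1). Expected progression of the disease is not an adverse event (Appendix 3).

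At stake are the absolute rates: incidence of breast cancer death biased down and BCSS biased up in both arms, with some loss of events from the Fine and Gray model.

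**Working it through.** **Plan's figure.** The documents give no event count, death rate or power for BCSS, so there is no BCSS figure to reproduce. The control-arm model used below does reproduce the plan's IBCFS figure. An 82% 4-year rate gives a hazard of -ln(0.82)/48 = 0.00413 per month. With HR 0.76, Table 12 accrual, 1% annual dropout and 3738 participants, it gives 568.3 expected events at month 60, against the stated 568.

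**Relative effect.** Let u be the share of breast cancer deaths after documented distant recurrence that are recorded as unknown cause. If u is constant over time and breast cancer deaths follow a documented distant recurrence, then

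reported incidence = (1 - u) x true incidence.

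The relative understatement is therefore u itself. It is an input and not a finding.

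**Absolute effect by month 60, control arm.** Assumptions not in the documents: 60% to 80% of IBCFS events are distant relapses, and survival afterwards is exponential with a median of 18 to 36 months. With the hazard above, Table 12 accrual and 1869 participants, deaths after distant relapse by month 60 number about 69 (60%, 36 months) to 143 (80%, 18 months). Adding 1% annual dropout gives about 67 to 140.

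| u | Deaths moved (u x 69 to u x 143) |
|---|---|
| 2% | 1.4 to 2.9 |
| 10% | 6.9 to 14.3 |
| 20% | 13.8 to 28.6 |

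In whole deaths the range is 1 to 29. As crude proportions, 1/1869 = 0.05% and 29/1869 = 1.55%, so roughly 0.1 to 1.6 percentage points. At u = 10%, 7/1869 = 0.37% and 14/1869 = 0.75%, or about 0.4 to 0.8 points.

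**Cumulative incidence in a separate illustration.** Assumed yearly hazards, control arm: distant recurrence 3% (below the 4% to 5% that section 2.2.8 gives for all IBCFS events), death after it 25%, other-cause death 1%.

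| u | 5 years | 10 years |
|---|---|---|
| 0 | 5.9% | 16.0% |
| 2% | 5.8% | 15.6% |
| 5% | 5.6% | 15.2% |
| 10% | 5.3% | 14.4% |
| 20% | 4.7% | 12.8% |

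With post-recurrence death hazards of 15% to 35% per year, the 10-year value is 12.2% to 18.2% at u = 0 and 11.0% to 16.4% at u = 10%.

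**Precision.** Losing a share u of events widens the log-scale confidence interval by about 1/sqrt(1 - u): 1.010 at 2%, 1.054 at 10% and 1.118 at 20%.

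**Hazard ratio.** In the same illustration, with distant recurrence reduced by 0.76 in the amcenestrant arm, the approximate 10-year ratio is 0.765 at u = 0 and 0.769 at u = 20% in both arms. It moves only if u differs by arm: 5% control against 10% amcenestrant gives 0.72, and 10% against 5% gives 0.81.

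**The case against.** The strongest reply is that the rule reaches only a residual category. The event is death attributable to breast cancer, and no section demands certification, so a site may use documented metastatic disease when it assigns the cause. Such deaths stay in BCSS. A reader might infer that deaths in metastatic breast cancer leave the endpoint; the definition does not support that.

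A reader might also infer from section 8.1.3 that cause of death is not collected. That passage is a short summary of visit purpose, and the case report form is not part of the document. BCSS cannot be computed without cause of death, and yearly contact delays news of a death without making its cause unknown. The size of u is therefore open and could be close to zero.

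It is fair, too, that the relative figures restate the assumed u, that not every unknown-cause death after relapse is from breast cancer, that nothing confirmatory rests on BCSS, and that the alternative swaps one misclassification for another. All of this stands and limits the point.

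The deferral to the SAP answers less. It covers sensitivity, supportive and subgroup analyses, names none for cause of death, and leaves the main rule as written. The document carries no SAP text on this endpoint, so whether a suitable sensitivity analysis is planned cannot be judged.

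**Conclusion.** The point holds in a conditional form, as a cheap improvement. The main BCSS rule classes unknown-cause deaths after documented distant recurrence against information the trial already holds. To the extent that such deaths occur and are from breast cancer, incidence is understated and BCSS overstated by the share u. For an assumed u of 2% to 20%, that is about 1 to 29 control-arm deaths by month 60, or roughly 0.1 to 1.6 percentage points, given the assumed distant share and post-relapse survival.

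It would go too far to say that breast cancer mortality is understated as a matter of fact, because the documents give no rate of unknown-cause deaths. It would also go too far to call the treatment comparison biased. With equal u the ratio stays near 0.77, and double blinding makes unequal u less likely. Equality is not guaranteed, since section 6.3 allows unblinding after recurrence with the sponsor's agreement. BCSS is outside the formal testing hierarchy, and IBCFS, IDFS, DRFS, LRRFS and OS count deaths of any cause, so none of them changes.

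**What to change.** In section 9.2.3.2, and in the SAP text that implements it:

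1. Count an unknown-cause death after documented distant recurrence as a breast cancer death.
2. Keep all other unknown-cause deaths as competing events.
3. Report the present rule as a sensitivity analysis.
4. Tabulate unknown-cause deaths by arm and by prior distant recurrence, which would also reveal any difference in u between arms.

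The cost is a wording change, one sensitivity analysis and one table, using recurrence data already collected for DRFS. The change should be made before the first database lock, the point by which section 9.2 requires the SAP to be final; later it would be post hoc. The downside is that a few deaths from other causes in participants with metastatic disease may be counted as breast cancer deaths. Comparing the two analyses shows how much the choice of rule matters.
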